4.3.2 Secondary Effectiveness Analyses

4.3.2.1 Distance Corrected Visual Acuity at Intermediate (66 cm)

Least Squares Means (LSMEANS) from the mixed effects model chosen during the model selection step will be employed to estimate the difference in means (AcrySof IQ PanOptix IOL Model TFNT00 minus AcrySof Monofocal IOL Model SN60AT) and the associated 95% (two-sided) confidence interval.

The first secondary superiority hypothesis will be deemed supported if the upper 97.5% confidence limit is less than 0.0 logMAR.

[figure not shown]
The SAS pseudo code is identical to the primary analysis.

[figure not shown]
4.3.2.2 IOLSAT Questionnaire

The second secondary endpoint will be analyzed by estimating the Mantel-Haenszel common difference in proportions (AcrySof IQ PanOptix IOL Model TFNT00 minus AcrySof Monofocal IOL Model SN60AT) along with the corresponding 95% (two-sided) confidence interval with site as a stratification variable. The superiority hypothesis will be deemed supported if the lower limit of the confidence interval exceeds zero.

SAS pseudo code for the above model is provided below.

[figure not shown]
```
proc freq data=IOLSAT;
  tables SITE*LENS_MODEL*IOLSATQ1 / riskdiff(common) alpha=0.05;
run;
```

4.4 Multiplicity Strategy

To account for multiplicity, the effectiveness hypotheses will be tested in sequence, two co-primaries, followed by first secondary, followed by second secondary. The primary effectiveness objective is considered met only if both co-primary hypotheses are met. The type I error for the non-inferiority test is 5% (1-sided) and for the superiority test is 2.5% (1-sided). Each of the secondary hypotheses will be tested at 2.5% (1-sided).

4.5 Handling of Missing Data

The AAS and BAS do not include any imputed values for the co-primary effectiveness endpoints, best corrected distance visual acuity and distance corrected near visual acuity. Although the influence of missing data is expected to be minimal, the following sensitivity analyses will be conducted to assess the impact of missing data on the conclusions from the co-primary effectiveness analyses.

1. Multiple imputation (with a fully conditional specification) method will be used to impute and estimate the treatment effect.

2. The sensitivity of inferences to departures from the missing-at-random (MAR) assumption will be examined using a pattern-mixture model approach (with a control-based pattern imputation^[3]).

Sensitivity Analysis 1:

A fully conditional specification (FCS) method will be used to impute missing monocular best corrected distance visual acuity at 4 m (first operative eye) values and monocular distance corrected visual acuity at near (first operative eye) at month 1 and month 6 visits in a data set with an arbitrary missing pattern. The FCS method uses a separate conditional distribution for each imputed variable.

The following SAS pseudo-code with the PROC MI procedure will be used to impute missing BCDVA values (or DCNVA) using FCS method:

```
/* multiple imputation w/ MAR assumption          */
/* BCDVA3-BCDVA4 should be in wide format      */
proc mi data=mi_in seed=1561 n impute=100 mu0=.1 .0 out=mi_out;
  fcs nbiter=100 reg; *reg(/details);
  var BCDVA3 BCDVA4;
run;
```

Sensitivity Analysis 2:

The sensitivity of inferences to departures from the MAR assumption will be examined using a pattern-mixture model approach with a control-based pattern imputation.

The following SAS pseudo-code with the PROC MI procedure will be used to implement the control-based pattern imputation:

```
/* multiple imputation w/ MNAR assumption          */
/* BCDVA3-BCDVA4 should be in wide format      */
proc mi data=mi_in seed=1561 n impute=100 mu0=.1 .0 out=mi_out;
  class LENS_MODEL;
  fcs nbiter=100 reg; *reg(/details);
  mnar model(BCDVA3 BCDVA4 / modelobs=(LENS_MODEL='SN60AT'));
  var BCDVA3 BCDVA4;
run;
```

Datasets obtained using each of the methods specified above will be analyzed using the model chosen for the primary analysis. The treatment effects and estimates of standard error obtained from each iteration within each method will be combined using PROC MIANALYZE and will be used to draw inferences about each sensitivity analysis. The SAS pseudo code to analyze the imputed datasets and combine the estimates is provided below.

```

/* run mixed model on each iteration of mi */
proc mixed data=mi_out;
  by _imputation_;
  class LENS_MODEL SITE;
  model BCDVA4 = LENS_MODEL /DDFM = satterth;
  random SITE SITE*LENS_MODEL; *[OR] random SITE;
  lsmeans LENS_MODEL / pdiff cl;
  estimate 'Trt_Eff' LENS_MODEL 1 -1;
  ods output Estimates = mimxd_out;
run;

/* generate estimates and CIs from multiple imputation */
proc mianalyze data = mimxd_out ;
  modeleffects estimate;
  stderr stderr;
  ods output ParameterEstimates = Param_out;
run;

```

For the second co-primary safety analysis, a sensitivity analysis imputing some missing data for contrast sensitivity measures is described in the corresponding section (5.3.2).

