5 AMENDMENTS

[figure not shown]
Modification of the protocol is prohibited without prior written agreement in the form of a protocol amendment. All amendments will be created by the Sponsor and must be approved by the Institutional Review Board (IRB)/ Independent Ethics Committee (IEC) prior to implementation except when required to mitigate immediate safety risks or when the changes involve only logistical or administrative revisions.

[figure not shown]

Section 12.3: Unscheduled Visits

[figure not shown]
Printed By:

[figure not shown]
Print Date:

6

SCHEDULE OF VISITS

Procedure/ Assessment	Visit 0	Visit 00	Visit 1	Visit 2	Visit 3	Visit 00A	Visit 1A	Visit 2A	Visit 3A	Visit 4A*		USV
	Screen (Day -30 to 0)	Implant 1	Day 1-2	Day 7-14	Day 30- 60	Implant 2	Day 1-2	Day 7-14	Day 30- 60	Part 1	Part 2	
Informed Consent	X											
Demographics	X											
Medical History	X											
Concomitant Medications	X	X	X	X	X	X	X	X	X	X	X	X
Inclusion/Exclusion	X	X				X						
Urine Pregnancy Test	X											
Administer Treatment(s)		X				X						
Device Deficiencies		X	X	X	X	X	X	X	X	X	X	X
Adverse Events (Both Volunteered and Elicited)	X	X	X	X	X	X	X	X	X	X	X	X

Procedure/ Assessment	Visit 0	Visit 00	Visit 1	Visit 2	Visit 3	Visit 00A	Visit 1A	Visit 2A	Visit 3A	Visit 4A*		USV
										Part 1	Part 2	
Procedure/ Assessment	Screen (Day -30 to 0)	Implant 1	Day 1-2	Day 7-14	Day 30- 60	Implant 2	Day 1-2	Day 7-14	Day 30- 60	Day 120-180 (from 2 nd eye)		N/A
Photopic Best Corrected Distance Visual Acuity (4m)	X			X	X			X	X	X, Xb		
Photopic Distance Corrected Intermediate Visual Acuity (66 cm)					X				X	X, Xb		
Photopic Distance Corrected Near Visual Acuity (40 cm)					X				X	X, Xb		
Distance Contrast Sensitivity – photopic										Xb		

Procedure/ Assessment	Visit 0	Visit 00	Visit 1	Visit 2	Visit 3	Visit 00A	Visit 1A	Visit 2A	Visit 3A	Visit 4A*		USV
										Part 1	Part 2	
Procedure/ Assessment	Screen (Day -30 to 0)	Implant 1	Day 1-2	Day 7-14	Day 30- 60	Implant 2	Day 1-2	Day 7-14	Day 30- 60	Day 120-180 (from 2 nd eye)		N/A
with glare												
Distance Contrast Sensitivity – photopic without glare										Xb		
Distance Contrast Sensitivity – mesopic with glare										Xb		
Distance Contrast Sensitivity – mesopic without glare										Xb		
QUVID questionnaire for visual disturbances) [†]	Xb									Xb	Xb	
IOLSAT questionnaire	Xb									Xb	Xb	

Procedure/ Assessment	Visit 0	Visit 00	Visit 1	Visit 2	Visit 3	Visit 00A	Visit 1A	Visit 2A	Visit 3A	Visit 4A*		USV

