2.1 Effectiveness Analysis Sets

The All-Implanted Analysis Set (AAS) includes all eyes with successful IOL implantation with at least one post-operative visit and will be the primary analysis set for all effectiveness analyses except [REDACTED] [REDACTED]

The Best-Case Analysis Set (BAS) will be the primary analysis set for [REDACTED] and contrast sensitivity, and includes all eyes successfully implanted that had:

- at least 1 post-operative visit;
- no preoperative ocular pathology;
- no macular degeneration detected at any time; and
- no major protocol deviations.

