4.6.2 Propensity Score Analysis

A propensity score is the conditional probability of being in the treatment group based on individual covariates at baseline. In a non-randomized study, baseline differences in covariates, amongst groups, may lead to a biased estimate of the treatment effect. To account for these differences the following two-step methodology outlined in (D'Agostino, 1998^[4]) will be employed.

Step 1: Fit a logistic regression model with the following baseline covariates to estimate the probability of being in the treatment group and creating the propensity score weights.

- 1) Age, continuous
- 2) Gender
- 3) Site
- 4) Baseline photopic best-corrected distance visual acuity

The SAS pseudo code for this step is provided below:

```
proc logistic data=Visual_acuity;
  where OPERATIVE_EYE = 'First' AND VISIT='VISIT4A';
  class SEX SITE LENS_MODEL;
  model LENS_MODEL (event='TFNT00') = AGE SEX SITE
    BCDVA_B /link=logit rsquare;
  output out=ps_set pred=ps;
run;

data ps_set;
  set ps_set;
  if TRT='TFNT00' then ps_weight=1/ps;
  else ps_weight=1/(1-ps);
run;
```

Step 2: Fit a propensity score-weighted linear regression model, using the GLM procedure.

```
proc glm data=ps_set;
  where OPERATIVE_EYE = 'First' AND VISIT='VISIT4A';
  class LENS_MODEL;
  model VA = LENS_MODEL /solution;
  weight ps_weight;
  lsmeans LENS_MODEL /pdiff cl;
  estimate 'Trt_eff' LENS_MODEL 1 -1;
run;
```

The estimated treatment effect from the above model will be compared to the estimated effect from the primary analysis mixed effects model. Meaningful differences will be investigated with additional exploratory analyses.

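### Both missing-data analyses in SAP 4.5 ignore first-eye acuity measured before Month 1, and Analysis 1 also omits lens group, so neither can detect or correct early dropout related to first-week vision.

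*SAP*

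**What the plan says.** SAP 4.5 plans two sensitivity analyses for missing co-primary data. Both impute acuity of the "first operative eye) at month 1 and month 6 visits in a data set with an arbitrary missing pattern". In each, the imputation variables are "var BCDVA3 BCDVA4", and the same code "will be used to impute missing BCDVA values (or DCNVA) using FCS method". The text names no other imputation variable.

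- **Analysis 1**, labelled missing at random (MAR), has no lens term and no BY statement. It fits one model to both lenses.
- **Analysis 2**, control-based, uses lens only to choose which eyes the model is estimated from: "mnar model(BCDVA3 BCDVA4 / modelobs=(LENS_MODEL='SN60AT".

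Of the step after imputation, the SAP says: "Datasets obtained using each of the methods specified above will be analyzed using the model chosen for the primary analysis".

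Three other places bear on this:

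- SAP 2.1: the All-Implanted Set "includes all eyes with successful IOL implantation with at least one post-operative visit". A visit at Day 1-2 or Day 7-14 is enough.
- Protocol section 6, Schedule of Visits: the row "Photopic Best Corrected Distance Visual Acuity (4m" is marked for the first eye at Visit 0, Visit 2 (Day 7-14), Visit 3 (Day 30-60) and Visit 4A. The near-acuity row starts at Visit 3.
- SAP 4.6.2 lists "Baseline photopic best-corrected distance visual acuity" as a propensity-score covariate, so the plan already treats it as an analysis variable.

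**The concern.** An MAR imputation is useful to the extent that it conditions on observed data that predict both dropout and outcome. For an eye lost before Month 1, both listed variables are missing, so the model has nothing from that eye to condition on. Yet its Week 1 BCDVA was scheduled, and that is the measurement closest to its departure.

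Subjects choose and know their lens (Protocol 7.2 and 11.4). Leaving early after disappointing first-week vision could therefore differ between the groups. If test-lens eyes with poor Week 1 acuity leave, the eyes that remain flatter the test lens on BCDVA. These analyses exist to show whether missing data matter to the co-primary conclusions, and for early leavers they cannot show it.

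The missing lens term in Analysis 1 adds a second error. Drawing early-lost eyes from a mixture of both lenses makes the arms look more alike. That is conservative for near-vision superiority. It is anti-conservative for BCDVA non-inferiority if the test lens is worse.

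**Working it through.** **1. The plan's own figures.** From SAP section 7: 113 completers per arm, SD 0.18, margin and superiority effect 0.10, one-sided alpha 0.05 and 0.025.

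- SE = 0.18 × √(2/113) = 0.0239; 0.10/0.0239 = 4.176.
- Non-inferiority power = Φ(4.176 − 1.645) = 99.4% (stated 99%).
- Superiority power = Φ(4.176 − 1.960) = 98.7% (stated 98%).
- Dropout: 125 × 0.9 = 112.5, against 113 required.

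**2. Pull toward zero when lens is omitted.** Let D be the completers' lens difference and d the fraction lost, equal in both arms and all before Month 1. Analysis 1 gives every lost eye the pooled mean m:

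[(1 − d)·μ_T + d·m] − [(1 − d)·μ_C + d·m] = (1 − d)·D

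Analysis 2 gives lost test eyes the control mean: (1 − d)·μ_T + d·μ_C − μ_C = (1 − d)·D. With d = 0.10 and D = −0.10, both give 0.9 × (−0.10) = −0.090. For early losses at equal dropout, the two checks therefore give the same expected answer.

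Simulation with random loss, 125 per arm, 10% missing per arm, all of it before Month 1, correlation 0.3, true difference −0.10:

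| Analysis | Lens difference |
|---|---|
| Completers | −0.0998 |
| Analysis 1 as written | −0.0903 |
| Analysis 1 with lens added | −0.0998 |
| Analysis 2 as written | −0.0901 |

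With the test lens worse by 0.10, completers give 0.098 and 0.102 (correlation 0.3 and 0.7) and Analysis 1 gives 0.088 and 0.092. That is a shift toward non-inferiority.

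**3. Bias from selective early loss, by hand.** Suppose the six test eyes with the worst Week 1 acuity leave. 6/125 = 4.8%; the normal cut-off is 1.665, with density 0.0998, so these eyes average 0.0998/0.048 = 2.08 SD above the mean. The other 119 shift by −6 × 2.08/119 = −0.105 SD at Week 1. At Month 6 the shift is −0.105 × 0.18 × ρ = −0.0189ρ: about −0.008, −0.011 and −0.015 for ρ = 0.4, 0.6 and 0.8. Completers carry this bias, and so does an imputation model with lens but no Week 1 value. If half of the 10% is lost early, pooling adds at least 0.05 × 0.10 = 0.005 in the same direction.

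**4. Both errors together, by simulation.** The sample size, SD, margin and approximate dropout are the plan's. The following are assumptions that the documents do not give: true difference at the margin (0.10); half of the losses before Month 1; early loss related to Week 1 acuity in the test arm only, ranging from moderate (odds multiplied by e per SD) to strong (the worst six leave); correlation 0.4 to 0.8 between visits; no site effects; records with both variables missing are imputed.

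| Imputation model | Bias (logMAR) | False non-inferiority in this check (nominal 5%) |
|---|---|---|
| As written | −0.011 to −0.020 | 9-22% |
| Lens added only | −0.004 to −0.015 | 5-16% |
| Week 1 added only | −0.002 to −0.006 | 5-7% |
| Both added | −0.002 or less | 4-6% |

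The completers' bias in the same scenarios is −0.004 to −0.015. If early loss is unrelated to Week 1 acuity, completers are about unbiased, the code as written is off by −0.005 to −0.008, and adding both terms does no harm.

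**The case against.** The strongest reply is that this concerns the choice of auxiliary variables in a supporting analysis. The non-inferiority decision rests on the unimputed mixed model of SAP 4.3.1. The SAP expects missing data to have little influence. The harmful scenario is assumed: nothing in the documents says that half the dropouts leave before Month 1, that Week 1 acuity drives loss in one arm only, or that the true difference lies at the margin. The plan assumes a difference of 0, and its SD of 0.18 is the maximum seen in an earlier study. All of that stands, and it limits the weight of the point. It does not explain leaving scheduled Week 1 data out of an analysis meant to condition on what was observed.

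A second reply is that the code is only pseudo-code. The text beside it, however, names the same two visits and nothing more.

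A reader might infer two stronger things that the documents do not support. One is that the MAR check simply reproduces the completers' result. That would need lens in the model; Analysis 1 lacks it and departs from completers toward zero. The other is that the trial's type I error is inflated to 9-22%. Those rates describe this check alone, under assumed selection at the margin.

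**Conclusion.** The point holds as an improvement to a sensitivity analysis. It follows from the documents that an eye lost before Month 1 is imputed from none of its own acuity in either analysis, and that Analysis 1 ignores lens. The two defects are separate. Adding lens alone leaves the selection bias that completers have; adding Week 1 alone leaves part of the pooling error.

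The size is modest. The worst bias, 0.020 logMAR, is 0.020/0.024 = 0.8 of a standard error and a fifth of the margin. If the true BCDVA difference is near the planned 0, the expected upper limit is about 1.645 × 0.024 = 0.04, and a bias of 0.02 would not change the conclusion. It matters if the true difference is near 0.10 and early dropout is selective. For near acuity the gain is smaller, since there is no measurement before Month 1, and the pull toward zero works against superiority.

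Some parts were not simulated: Analysis 2 under selective loss, the contribution of Visit 0 BCDVA, and the variable list for near acuity. How the software handles a record with every listed variable missing is not stated. If it drops such records, their own acuity still goes unused.

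**What to change.** In SAP 4.5, before database lock:

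- **Both PROC MI steps:** add first-eye BCDVA at Visit 0 and Visit 2. For BCDVA the list becomes `BCDVA0 BCDVA2 BCDVA3 BCDVA4`. For DCNVA use `BCDVA0 BCDVA2 BCDVA3 DCNVA3 DCNVA4`.
- **Analysis 1:** also add `LENS_MODEL` as a class predictor in the variable list, or impute separately by lens. Analysis 2 keeps its control-based restriction.
- **`mu0` option:** drop it or extend it, since it holds two values and the list will be longer.
- **Text:** name the imputation variables in the prose as well as in the code.

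The cost is a few lines of SAP text and code. It needs no new subjects, visits or measurements and leaves the primary analysis unchanged. FCS already handles gaps in the added variables.

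### SAP 4.5's imputation labelled MAR leaves out lens, and both missing-data checks on average shrink a BCDVA lens difference that is similar at Months 1 and 6

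*SAP*

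**What the plan says.** The primary analysis imputes nothing. Protocol 15.5 promises sensitivity analyses for missing data and leaves the details to the SAP. SAP 4.5 states their purpose: "sensitivity analyses will be conducted to assess the impact of missing data on the conclusions from the co-primary effectiveness analyses". It adds a qualifier: "Although the influence of missing data is expected to be minimal".

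- **Sensitivity Analysis 1 (SA1)** carries the code comment "multiple imputation w/ MAR assumption". Its variable list is "var BCDVA3 BCDVA4". The step has no CLASS or BY statement, and the surrounding text does not mention lens. The same code serves both co-primaries; the SAP says it "will be used to impute missing BCDVA values (or DCNVA) using FCS method".
- **Sensitivity Analysis 2 (SA2)** is described as control-based: "The sensitivity of inferences to departures from the MAR assumption will be examined using a pattern-mixture model approach with a control-based pattern imputation". It is coded "mnar model(BCDVA3 BCDVA4 / modelobs=(LENS_MODEL='SN60AT" (closing characters omitted here). Only SN60AT eyes inform the imputation.
- **Analysis of the imputed data** uses "model BCDVA4 = LENS_MODEL /DDFM = satterth", so a lens effect is estimated in both.

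Under SAP 4.3.1, BCDVA non-inferiority holds if the upper 95% limit of TFNT00 minus SN60AT is below 0.10 logMAR. Section 4.5 contains no delta-adjusted or tipping-point run.

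**The concern.** An imputation model that omits the factor whose effect is then estimated treats the two groups as one when filling gaps. SA1 therefore does not impute under MAR given lens, which is what the lens comparison needs. SA2 borrows from the control arm by design. When the lens difference is similar at both visits, each moves the estimate toward zero on average.

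For DCNVA superiority that direction is cautious. For BCDVA non-inferiority it helps the test lens in the one situation where the margin is under threat, namely TFNT00 worse at distance. Neither check lets missing TFNT00 eyes do worse than pooled or control-type eyes with the same Month 1 acuity. What is at stake is how informative the two checks are for BCDVA. The success decision itself is not affected.

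**Working it through.** **Inputs.** From SAP 7: SD 0.18 logMAR (s² = 0.0324), margin 0.10, planned BCDVA difference 0, about 125 per arm with 113 completers, about 10% dropout. Assumed, because the documents do not say: Month 1 to Month 6 correlation ρ of 0.3 to 0.7, equal SD at both visits, missingness unrelated to outcome and equal by arm, Month 1 observed unless stated, no site effect.

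**The plan's own figure.** SE = 0.18·√(2/113) = 0.02395. Power = Φ(0.10/0.02395 − 1.645) = Φ(2.53) = 99.4%, against 99% stated. It is reproduced and not disputed.

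**Average shrinkage.** Let d be the lens difference at both visits and p the fraction missing per arm.

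- SA1: the pooled slope is b = (ρs² + d²/4)/(s² + d²/4). Imputed eyes differ by b·d, so the estimate averages d·[1 − p(1 − b)].
- SA2: imputed test eyes average ρ·d above control, so the estimate averages d·[1 − p(1 − ρ)].
- Imputing within lens: imputed eyes differ by d, with no shrinkage.

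At d = 0.06 and p = 10%:

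| ρ | b | SA1 shrinkage | SA2 shrinkage |
|---|---|---|---|
| 0.3 | 0.319 | 6.8% | 7% |
| 0.5 | 0.514 | 4.9% | 5% |
| 0.7 | 0.708 | 2.9% | 3% |

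At ρ = 0.5, missing test eyes average 0.060 within lens, 0.030 + 0.514 × 0.030 = 0.045 under SA1, and 0.5 × 0.060 = 0.030 under SA2. If Month 1 is also missing, imputed eyes carry no lens difference and the shrinkage is p itself, about 10%.

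**Upper limit at d = 0.05, 12 of 125 missing per arm (p = 0.096).** Primary: 0.05 + 1.645 × 0.02395 = 0.0894. For imputed data, T = 2s²/125 + 1.01·B, with B = 2p²(1 − ρ²)s²(1/12 + 1/113). At ρ = 0.5, √T = 0.02367 and 1.645·√T = 0.03893.

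- SA1: 0.04765 + 0.03893 = 0.0866
- SA2: 0.04760 + 0.03893 = 0.0865
- Within lens: 0.05 + 0.03893 = 0.0889

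Over ρ = 0.3 to 0.7, SA1 and SA2 each give 0.0859 to 0.0870, and within lens gives 0.0885 to 0.0892.

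**Simulation** (125 per arm, 12 missing per arm, 20 imputations, Rubin's rules). With a true deficit of 0.10 at both visits, 6,000 trials per ρ and Monte Carlo SE 0.3 points, non-inferiority was wrongly shown as follows:

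| ρ | Observed data | SA1 | SA2 | Within lens |
|---|---|---|---|---|
| 0.3 | 5.1% | 6.8% | 7.0% | 5.1% |
| 0.5 | 4.7% | 5.4% | 5.5% | 4.6% |
| 0.7 | 4.9% | 5.6% | 5.6% | 5.0% |

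A separate simulation (1,200 trials, 12 imputations, ρ = 0.5) with Month 1 also missing for every dropout gave 8.6% (SA1) and 8.3% (SA2), against 5.2% for observed data. Mean estimates were 0.090, 0.090 and 0.100.

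**Where the direction fails or vanishes.**

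- Single trials: with a true deficit of 0.05 at both visits, the upper limit moved closer to 0.10 in about 14% to 34% of trials that had an observed deficit.
- Unequal visits: SA2 gives missing test eyes ρ times the Month 1 difference. This exceeds the Month 6 difference when Month 1 is more than 1/ρ times as large, which is twice at ρ = 0.5. Simulated with 0.15 at Month 1 and 0.05 at Month 6, SA1 averaged 0.0505 and SA2 0.0510, against 0.0483 for observed data.
- True difference 0: no shift. True difference −0.05, half the dropouts also without Month 1: both averaged −0.046, slightly against non-inferiority.

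**The case against.** **The effect is small and rests on assumptions.** This stands. The documents give no correlation, no missingness by arm and no Month 1 completeness. At ρ of 0.5 and 0.7 the rise in false passes is under one percentage point. Part of the fall from 0.0894 is not caused by omitting lens, since correct within-lens imputation already gives 0.0885 to 0.0892.

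**It is only pseudo-code.** Lens could be added in programming. However, the SAP says this code will be used, and no text tells the programmer to add lens. SA2's code has a CLASS LENS_MODEL line and SA1's does not.

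**SA2 does what it says.** This also stands. It is announced as control-based, cites a method reference, and is coded accordingly. No passage promises a tipping-point run, so the absence of one is not a breach of the plan.

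Three stronger readings are tempting and not supported:

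- A reader might infer that whenever TFNT00 is observed to be worse, both checks must report an upper limit further from the margin. The single-trial and unequal-visit results above show that this holds only on average and under a condition.
- A reader might infer that a non-inferiority result would be fragile from an observed deficit of about 0.04. At that deficit all 12 missing TFNT00 eyes would have to be a further 0.21 logMAR worse for the limit to reach 0.10, which is more than one SD. SAP 7 calls 0.18 the maximum variability seen in an earlier study; a smaller SD would require a larger shift still.
- A reader might infer that the trial's type I error is inflated. The decision uses the primary model without imputation, so it is not.

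**Conclusion.** The concern holds in a limited form. SA1 is coded wrongly for its stated purpose: it is labelled MAR, omits lens, and feeds an analysis that estimates a lens effect. SA2 is correctly coded, but as a check on non-inferiority it shares the same average direction.

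If the lens difference is similar at both visits, the average shrinkage is about 3% to 7% at 10% missing with Month 1 observed and ρ of 0.3 to 0.7, and larger if Month 1 is missing. In the worked case of a 0.05 deficit, this lowers the upper limit by about 0.0015 to 0.0033 logMAR relative to within-lens imputation. So on average neither check stresses the BCDVA non-inferiority conclusion, while both are cautious for DCNVA. This is a minor improvement to two supporting analyses. The sample size, the primary analysis and the success criteria are not in question.

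**What to change.** **Change:** in SA1, add LENS_MODEL to CLASS and VAR, or impute BY LENS_MODEL, for both BCDVA and DCNVA. In the simulations this removed the pull and returned the false-pass rate to that of the observed data.

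**Optional:** keep the control-based analysis for DCNVA. For BCDVA, add a delta-adjusted run: impute within lens, worsen the imputed TFNT00 Month 6 values in fixed steps before the PROC MIXED step, and report the shift at which the upper 95% limit reaches 0.10 logMAR. To show what it would report, solve d + p·D + 1.645·√T = 0.10 for the shift D, with the test-arm variance raised to s² + p(1 − p)D². At ρ = 0.5 and 12 missing per arm, D is 0.56 at an observed deficit of 0 and 0.11 at 0.05. A large value would support the sponsor's expectation that missing data matter little.

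**Cost:** a few lines of code and one or two SAP sentences. No new data are needed, and the primary analysis does not change.

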4.3.1 Primary Effectiveness Analyses

Least Squares Means (LSMEANS) from the mixed effects model chosen during the model selection step will be employed to estimate the difference in means (AcrySof IQ PanOptix IOL Model TFNT00 minus AcrySof Monofocal IOL Model SN60AT) and the associated 90% (two-sided) confidence interval for the non-inferiority test and 95% (two-sided) confidence interval for the superiority test.

The non-inferiority hypothesis (first co-primary) will be deemed supported if the upper 95% confidence limit is less than the non-inferiority margin of 0.10 logMAR.

The superiority hypothesis (second co-primary) will be deemed supported if the upper 97.5% confidence limit is less than 0.0 logMAR.

SAS pseudo code for the above models is provided below.

```
proc mixed data=visual_acuity;
  where OPERATIVE_EYE = 'First' AND VISIT='VISIT4A';
  class LENS_MODEL SITE;
  model VA = LENS_MODEL /DDFM = satterth;
  random SITE SITE*LENS_MODEL; *[OR] random SITE;
  lsmeans LENS_MODEL / pdiff cl;
  estimate 'Trt_Eff' LENS_MODEL 1 -1;
run;
```

An analysis with a mixed-effect model analysis of variance (ANOVA) accounting for correlation between the first and the second eye will be performed as a sensitivity analyses. The following SAS pseudo code will be used:

```
proc mixed data=visual_acuity;
  where VISIT='VISIT4A';
  class LENS_MODEL SITE OPERATIVE_EYE;
  model VA = LENS_MODEL /DDFM = satterth;
  random SITE SITE*LENS_MODEL; *[OR] random SITE;
  repeated OPERATIVE_EYE / subject=USUBJID(SITE) TYPE=CS;
  lsmeans LENS_MODEL / pdiff cl;
  estimate 'Trt_Eff' LENS_MODEL 1 -1;
run;
```

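### The pooling code for the missing-data sensitivity analyses drops the Satterthwaite degrees of freedom, leaves the interval level unset and pools the contrast in reverse; the error is minor but worth correcting

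*SAP*

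**What the plan says.** SAP 4.3.1 defines the treatment difference as TFNT00 minus SN60AT and prescribes the "associated 90% (two-sided) confidence interval for the non-inferiority test and 95% (two-sided) confidence interval for the superiority test". Non-inferiority on BCDVA holds if the "upper 95% confidence limit is less than the non-inferiority margin of 0.10 logMAR"; superiority on DCNVA holds if the upper 97.5% limit is below zero. SAP 4.4 gives the matching error rates: "The type I error for the non-inferiority test is 5% (1-sided) and for the superiority test is 2.5% (1-sided").

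SAP 4.5 plans two multiple-imputation analyses, one under missing-at-random and one control-based, each with 100 imputations, to test the co-primary conclusions against missing data. Its prose says that the imputed data sets are analysed with the model chosen for the primary analysis, and that the combined results are the basis of inference for each sensitivity analysis. The printed code does the following:

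- It fits "model BCDVA4 = LENS_MODEL /DDFM = satterth" within each imputation, with random effects for site plus site-by-lens, or for site alone.
- It forms the contrast "estimate 'Trt_Eff' LENS_MODEL 1 -1" and saves only the Estimates table.
- It pools that table with "proc mianalyze data = mimxd_out", naming the estimate and its standard error. No EDF= or ALPHA= option appears.

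The lens values can be read from the code: "modelobs=(LENS_MODEL='SN60AT" in SAP 4.5, and `TFNT00` in the propensity model of SAP 4.6.2.

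**The concern.** A sensitivity analysis should differ from the primary analysis only in how it treats the missing values. Here the pooling step changes three other things: the reference distribution, the interval level for BCDVA and the sign of the contrast. A difference between the primary result and the imputed result could then come from the code and be mistaken for an effect of missing data, or could hide one.

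The degrees of freedom are the least visible of the three. If the treatment effect is judged against between-site variation, the primary analysis uses a t multiplier with few degrees of freedom, while the pooled analysis uses what is in effect a normal multiplier. The check on DCNVA could then look firmer than the result it is meant to stress.

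**Working it through.** **Inputs from the documents.** One-sided alpha 0.05 and 0.025 (SAP 4.4); 90% and 95% two-sided intervals (SAP 4.3.1); 113 completers per group and SD 0.18 logMAR (SAP 7); 100 imputations (SAP 4.5); about 12 sites (Protocol 10).

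**Assumptions not in the documents.** PROC MIANALYZE defaults to infinite complete-data degrees of freedom and ALPHA=0.05; CLASS levels are taken in sorted order; missing information λ is 3-8%; the arms are balanced within site; complete-data df is about 12 − 1 = 11 under the lens-by-site model with non-zero interaction variance, and about 213 under the site-only model.

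**Plan's own figures.** SE = 0.18 × √(2/113) = 0.0239, and 0.1/0.0239 = 4.18.

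- Non-inferiority power: Φ(4.18 − 1.645) = 99.4% (stated 99%).
- Superiority power: Φ(4.18 − 1.96) = 98.7% (stated 98%).

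Both reproduce.

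**Degrees of freedom.** Without EDF=, the pooled df is (m − 1)(1 + 1/r)², with m = 100 and r = λ/(1 − λ). This gives 110,000 at λ = 3% and about 15,500 at λ = 8%, so the multipliers are effectively 1.645 and 1.960. With EDF = ν₀, the Barnard-Rubin form combines that df with (1 − λ)ν₀(ν₀ + 1)/(ν₀ + 3). For ν₀ = 11 the second term is (1 − λ) × 132/14 = (1 − λ) × 9.43, and the combined df is 9.1 to 8.7.

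| Model | Pooled df | Upper 95% multiplier | Upper 97.5% multiplier | Actual tail at 1.645 | Actual tail at 1.96 |
|---|---|---|---|---|---|
| Lens-by-site, ν₀ = 11 | 8.7-9.1 | 1.83-1.84 | 2.26-2.28 | 6.7-6.8% | 4.1% |
| Site only, ν₀ = 213 | 192-204 | 1.65 | 1.97 | 5.1% | 2.6% |

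For DCNVA under the lens-by-site model, 1 − 1.96/2.26 = 13% too narrow. From 15 sites down to 8, the shortfall runs from 10% to 23%.

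**Level, BCDVA only.** The default interval gives an upper 97.5% limit where the rule needs an upper 95% limit: 1.96/1.645 = 1.19, so 19% too wide under normal multipliers. The largest observed difference that passes is 0.10 − 1.96 × 0.0239 = 0.053 logMAR, against 0.10 − 1.645 × 0.0239 = 0.061. Under the lens-by-site model the two omissions partly offset. The printed 1.96 exceeds the required 1.83, so the tail is 4.1% against an allowed 5%. At 8 sites they roughly cancel (tail 5.1-5.3%). Setting 90% without EDF= would remove the offset and leave the limit 1 − 1.645/1.83 = 10% too narrow at 12 sites.

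**Direction.** `SN60AT` sorts before `TFNT00`, so coefficients 1 -1 give SN60AT minus TFNT00. With the planned DCNVA benefit of 0.10, the printed upper limit centres on 0.100 + 1.96 × 0.0239 = +0.147. Applied literally, the rule that the limit be below zero would essentially never be met. With the test lens 0.13 logMAR worse on BCDVA, the printed upper limit centres on −0.13 + 1.96 × 0.0239 = −0.083, which is below 0.10; the correct upper 95% limit is 0.13 + 1.645 × 0.0239 = +0.169.

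**The case against.** The strongest reply is that the code is labelled pseudo-code and is visibly schematic: it shows alternative random effects and only the BCDVA variable. The prose governs. SAP 4.3.1 fixes direction and levels, SAP 4.5 refers back to the primary model, and the primary code also omits a 90% setting although its text requires one. This largely answers the level and direction points, since a 90% limit and a reversed sign can both be obtained from the pooled estimate and standard error. It does not answer the degrees-of-freedom point, because no prose says which df the pooled limits should use and the code is the only specification of that step.

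Three stronger readings are tempting, and the documents do not support them.

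- A reader might infer that the reversed contrast would let an inferior lens pass non-inferiority. That requires applying a test-minus-control rule to a control-minus-test result unnoticed. The stated direction is clear, and the same code would show the expected DCNVA benefit with the wrong sign, so the error would reveal itself. Nor is it peculiar to pooling: the same coefficients stand in both code blocks of SAP 4.3.1 and in SAP 4.6.2.
- A reader might infer that the BCDVA check runs at 6.7% error. That figure belongs to a 90% interval without EDF=, which is not what is printed.
- A reader might infer that trial success is at risk. Success rests on the primary analysis; SAP 4.5 has no decision gate and no alpha allocation.

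The df effect is also conditional on BIC choosing the lens-by-site model with non-zero variance. Even then its practical weight is small at the planned effect: using the SE of 0.0239, which ignores interaction variance, moving from 1.96 to 2.26 lowers the chance of passing DCNVA from 98.7% to 97.2%.

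**Conclusion.** This is a minor but real code error, confined to the missing-data sensitivity analyses. The degrees-of-freedom loss stands conditionally: about 13% too narrow and about 4.1% nominal one-sided error for DCNVA under the lens-by-site model, and negligible under the site-only model. The BCDVA level mismatch stands, and is conservative as printed at about 12 sites. The contrast is opposite in sign to the stated difference in SAP 4.3.1, 4.5 and 4.6.2, and can be recovered without loss.

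The sizes depend on the assumed SAS defaults, the number and balance of sites, and the assumed missing information. The error rates describe how the limits are calibrated; a sensitivity analysis is not a confirmatory test. The stated rules for the primary tests, their power and the sample size are unaffected.

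**What to change.** Amend the SAP code before the analysis is run:

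1. In SAP 4.5, pass the complete-data df from the MIXED Estimates table to PROC MIANALYZE through EDF=. State in advance how one value is taken across imputations, for example the smallest or the average.
2. In the same step, set ALPHA=0.10 for BCDVA and ALPHA=0.05 for DCNVA. Do this together with item 1, because setting 90% alone would make the BCDVA limit too narrow under the lens-by-site model.
3. Write the contrast as `LENS_MODEL -1 1` in both blocks of SAP 4.3.1, in SAP 4.5 and in SAP 4.6.2. Changing only SAP 4.5 would give the sensitivity code the opposite sign to the primary code.

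The cost is a few lines of code and no new data. The one downside is slightly wider DCNVA sensitivity limits if the lens-by-site model is selected; the BCDVA limits move to the level that SAP 4.3.1 already states.
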